6.5. Exploratory Endpoint Analysis

The exploratory endpoints include the number of choices for cigarette puffs and e-cig puffs, number of choices to abstain from puffing, CES, Perceived Health risks, QSU, MNWS, PANAS, measures of cardiovascular function and biomarkers. We expect that biomarkers of exposure, and possibly other endpoints, will be skewed and will be log-transformed for analysis. These variables will be summarized using the geometric mean and differences between groups will be summarized by ratios of geometric means and 95% confidence intervals (CI). Any measurement that is obtained multiple times across lab sessions will be analyzed using a linear mixed model to

account for the within subject effect. Drop-out rates will be compared between the two cigarette groups with a chi-squared test.

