Lab Sessions 2-5 will each include a preference task in which two products are available. In the sampling phase, participants will sample and then rate the same combusted cigarette type from Lab Session 1 and will also sample and rate an e-cig with the assigned combination of characteristics for that session (i.e., 3 mg/mL nicotine + cigarette flavor; 3 mg/mL nicotine + non-cigarette flavor; 18 mg/mL nicotine + cigarette flavor; or 18 mg/mL nicotine + non-cigarette flavor). E-liquid nicotine concentration will be administered under double-blind conditions; flavors, by necessity, will not be blinded. In the preference phase, participants will be prompted via computerized instructions to make a series of 10 choices. Each choice will be to either take 2 cigarette puffs, 2 e-cig puffs, or to abstain from puffing; again, a total of 20 puffs (from either or both products) is available (tasks are described in greater detail below). Between lab sessions, participants will be instructed to return to their usual tobacco use patterns.

Design Schematic					
NNC cigarettes (n=60): 5 sessions			VLNC cigarettes (n=60): 5 sessions		
e-liquid nic concentration	e-liquid flavors	e-liquid flavors	e-liquid nic concentration	e-liquid flavors	e-liquid flavors
3 mg/ml	x	x	3 mg/ml	x	x
18 mg/ml	x	x	18 mg/ml	x	x
No e-cig	x		No e-cig	x	

Summary of Measures

MEASURES	SCREEN/ BL	LAB SESSIONS				
		1	2	3	4	5
QUESTIONNAIRES AND MONITORING						
Demographics Questionnaire	X					
Medical History Questionnaire & Follow-Up Questionnaire	X					
MINI Suicide Subscale	X					
Tobacco Use History Questionnaire	X					
Vaping History Questionnaire	X					
Timeline Follow Back (TLFB): Baseline and Lab Session Versions	X	X	X	X	X	X
Contemplation Ladder	X					
Drug Use History Questionnaire	X					
Depressive Symptoms (CES-D)	X					
Fagerstrom Test for Nicotine Dependence (FTND)	X					
Cigarette Dependence Questionnaire	X					
Environmental Tobacco Smoke (ETS) Questionnaire	X					
Smoking/Vaping Identity	X					
Smoking Expectancies Questionnaire	X					
Respiratory Health (ATSQ)	X					
Predicted Behavior Interview						X
Adverse Events		X	X	X	X	X
End of Study Questionnaire						X
LABORATORY PREFERENCE TASK						
Questionnaire on Smoking Urges (QSU)- Brief	X	X	X	X	X	X
Minnesota Nicotine Withdrawal Scale (MNWS)	X	X	X	X	X	X
Positive and Negative Affect Scale (PANAS)	X	X	X	X	X	X
Cigarette Evaluation Scale (CES)	X	X	X	X	X	X
Vaping Expectancies Questionnaire (VEQ)	X					

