- 6) Perceived Health Risks Scale (PHRS; Hatsukami et al., 2015), a measure of the perceived addictive potential and other health risks associated with cigarettes
- 7) Positive and Negative Affect Schedule (PANAS; Watson, Clark, & Tellegan, 1988), which measures symptoms of positive and negative affect
- 8) Minnesota Nicotine Withdrawal Scale (MNWS; Hughes & Hatsukami, 1986), a measure of nicotine withdrawal
- 9) Questionnaire of Smoking Urges-Brief – Usual Brand Cigarette (QSU; Cox, Tiffany, & Christen, 2001; Tiffany & Drobes, 1991), which measures the urge to smoke
- 10) Cigarette Evaluation Scale (CES; Westman, Levin, & Rose, 1992; Cappelleri, et al., 2007), which measures responses to cigarettes (e.g., reward, satisfaction)
- 11) Smoking Expectancies Questionnaire, which will be used to understand factors that motivate adolescents to smoke cigarettes.
- 12) Vaping Expectancies Questionnaire (VEQ), which assesses participant's expectancies regarding the use of vaping devices
- 13) Vaping Device Utility Questionnaire, an assessment of the reasons for using vaping devices
- 14) Cigarette Purchase Task – Usual Brand Version (Jacobs & Bickel, 1999; MacKillop et al., 2008) which will be used to generate cigarette demand curves. Participants will be asked to report the number of cigarettes that they would consume in a day at various costs. Several indices of demand are generated from the raw values, including demand intensity (consumption at zero price), Omax (maximum amount of money allocated to cigarettes), breakpoint (the first price at which a subject reports zero consumption) and Pmax (the price at which Omax occurs). This task will indicate whether prolonged VLNC cigarette use reduces cigarette demand and increases sensitivity to increases in cigarette costs.

Biological specimens collected, stored, and entered into CENIC Biosample Collection Platform:

- 1) **Saliva sample for NMR assessment:** Participants will be asked to provide two saliva samples during Baseline for assessment of nicotine metabolite ratio (NMR), an indicator of CYP2A6 enzyme activity (Benowitz, et al., 2003). Participants must wait 30 minutes after arrival to the lab before collecting the two saliva samples. During this time, participants cannot eat, drink, chew gum or smoke cigarettes. Samples will be stored at temperatures no more than -20°C. Saliva samples will be sent regularly to be analyzed and stored at the University of Minnesota.

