Demographics and baseline data will be compared between the groups randomized to NNC or VLNC cigarettes using t-tests and chi-square tests. The endpoints of interest are the number of puffs from cigarettes, the number of puffs from e-cigs, and the number of choices to abstain from both cigarettes and e-cigs. Descriptive statistics will summarize the data by cigarette group and by session. Results will be presented in tabular and graphical format.

The **primary aim** is to examine the effects of cigarette nicotine content, e-cig nicotine concentration and e-cig flavor on choices to smoke. The primary outcome measure is the number of cigarette puffs, and the secondary outcomes are the number of e-cig puffs, and CO boost.

The **secondary aim** is to examine the effects of these factors on product appeal and sensory effects (Cigarette/E-Cig Evaluation Scale), perceived health risks (Perceived Health Risks Assessment), and pre- to post-use changes in craving (QSU), withdrawal symptoms (MNWS), and affect (PANAS). The primary statistical model to test both aims will be a linear mixed model carried out according to the $2 \times 2 \times 2$ design, where the between-subject factor is NNC or VLNC cigarettes and the two within-subject factors relate to e-cig flavor (cigarette or non-cigarette) and nicotine concentration (very low or moderate). The session where no e-cigs are included will be analyzed separately by comparing choices for NNC vs. VLNC cigarettes using a two sample t-test with unequal variances. The mixed model for the balanced factorial design will allow for the evaluation of the three main effects and their interactions. The major concern for this

approach is the occurrence of non-constant variance for the number of puffs of each product or the number of times abstaining as the dependent variables. Therefore, sensitivity analyses will be performed to evaluate the robustness of our assumptions. A generalized estimating equation (GEE) model uses sandwich estimators and thus is less affected by unequal variances, however, it is more negatively impacted by the occurrence of missing observations. Additionally, a negative binomial regression approach will check if modeling the number of puffs as a count variable provides a better fit to the data. The first mixed model will assume that participant characteristics are balanced between groups due to randomization and include only the three main effects and their interactions.

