6.4. Secondary Endpoint Analysis

Secondary endpoints will be summarized by cigarette group and lab session using the mean and standard deviation. Number of puffs of e-cigs taken are measured in sessions 2 to 5, where e-cigs are available. CO boost (i.e., post-choice CO minus pre-choice CO) is measured at every session (1 to 5). The analysis of the secondary endpoints will be a linear mixed model following the same 2 x 2 x 2 factorial design outlined in section 6.3.1. First with only main effects and interaction terms along with the stratification and the baseline values to increase precision, and then a second model adding in any important baseline characteristics as potential moderators of study outcomes.

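### SAP 6.5 names no baseline or stratification covariate for the subjective scales, which gives up some precision for the NNC versus VLNC contrast only

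*Combined protocol and SAP*

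**What the plan says.** The protocol's Statistical Approach sets the secondary aim as effects on "product appeal and sensory effects (Cigarette/E-Cig Evaluation Scale), perceived health risks (Perceived Health Risks Assessment") and on "pre- to post-use changes in craving (QSU), withdrawal symptoms (MNWS), and affect (PANAS"). It adds: "The primary statistical model to test both aims will be a linear mixed model". Its first model is to "include only the three main effects and their interactions". Later protocol models bring in gender, baseline CPD and dependence as moderators, not the baseline value of the scale.

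SAP section 2 keeps subjective effects as the secondary aim, but SAP 5.3 lists the scales, with the CPT, as exploratory endpoints. SAP 6.5 then gives the rule "Any measurement that is obtained multiple times across lab sessions will be analyzed using a linear mixed model", to handle within-subject correlation. It names no baseline score and no stratification variable, and does not say whether the outcome is a post-use score or a change.

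The neighbouring sections do name covariates. SAP 6.3.1 adds gender, menthol status, baseline CPD and Session 1 puffs. SAP 6.4 adds the stratification variables "and the baseline values to increase precision".

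The scores exist. The Summary of Measures and the Baseline Procedures list QSU, MNWS, PANAS, CES, PHRS and CPT at Screening/Baseline. The CES there is described as a scale "which measures responses to cigarettes (e.g., reward, satisfaction"), and the QSU and CPT are usual-brand versions. Randomisation follows, at Lab Session 1. QSU, MNWS and PANAS are also taken before the task at every lab session. CES, PHRS and CPT are completed in the lab only after sampling.

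**The concern.** The NNC versus VLNC effect on a rating scale compares different people. Part of its error is each person's stable way of scoring, and a score taken before randomisation can remove some of that. The SAP accepts this reasoning for puffs and CO boost, but stops short of the scales that answer its own secondary aim.

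The open outcome definition adds a second question. If QSU, MNWS and PANAS were analysed as simple post-minus-pre differences, the pre-score would be used, but less efficiently than as a covariate. At stake is precision, not bias: with randomisation the unadjusted arm contrast is unbiased.

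**Working it through.** **Inputs.** From SAP 3.2: 60 per group, between-group effect size (ES) 0.60, two-sided alpha 0.05, power at least 90%. The correlation r between baseline score and outcome is not in the documents, so a range is assumed.

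**1. The plan's own figure.** Two-sample t-test: noncentrality 0.60 × √(60/2) = 3.286 on 118 df gives power 90.3%. The stated 90% reproduces. No power is stated for the scales themselves.

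**2. Baseline covariate against an unadjusted post score, one session.** Residual variance is multiplied by 1 − R², with R² = r². The effective ES becomes 0.60/√(1 − R²), and the equivalent unadjusted sample is 120/(1 − R²).

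| R² (assumed) | Effective ES | Noncentrality | Power | Equivalent N |
|---|---|---|---|---|
| 0 | 0.600 | 3.286 | 90.3% | 120 |
| 0.04 | 0.612 | 3.354 | 91.4% | 125 |
| 0.10 | 0.632 | 3.464 | 93.0% | 133 |
| 0.20 | 0.671 | 3.674 | 95.4% | 150 |
| 0.30 | 0.717 | 3.928 | 97.4% | 171 |

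**3. Covariate adjustment against raw change (QSU, MNWS, PANAS), one session.** With equal variances s² and pre-post correlation rho, the change has variance 2s²(1 − rho) and the adjusted post score s²(1 − rho²). The ratio is (1 + rho)/2: 0.65, 0.75 and 0.85 at rho 0.3, 0.5 and 0.7, so 35%, 25% and 15% less variance. This uses a different comparator from step 2, and the two gains must not be added.

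**4. Mean of Sessions 2–5.** With between-session correlation 0.5 (assumed), the variance of a person's mean is (1 + 3 × 0.5)/4 = 0.625 in units of s². A baseline score with r = 0.5 leaves 0.625 − 0.25 = 0.375, which is 40% less. With r = 0.3 it leaves 0.535, which is 14% less.

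**5. E-cig nicotine and flavor main effects.** These are within-person contrasts. With complete data, a score that is constant within a person cancels, and simulation with 120 people gave a variance ratio of 1.00. Only a session-specific score can help. At within-person pre-post correlations of 0, 0.3, 0.5 and 0.7, adjusting for the same-session pre-task score gave variance ratios of 1.01, 0.92, 0.76 and 0.51 against the unadjusted post score. Raw change gave 2.00, 1.41, 1.00 and 0.60.

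**6. Which ratings have a usable score.** For the study-cigarette CES, PHRS and CPT there is a Screening/Baseline cigarette or usual-brand version. For QSU, MNWS and PANAS there is Screening/Baseline and the Session 1 pre-task score. For the vaping-device CES, PHRS and CPT none is listed; the baseline vaping questionnaires (expectancies, device utility) are different instruments.

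**The case against.** Several objections have force.

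- **Status.** The SAP classes these endpoints as exploratory and claims no power for them, so this is an improvement, not the repair of an invalid analysis.
- **Silence.** Naming no covariate is not the same as excluding one, and the protocol assigns one model to both aims. But that protocol model holds only the factorial terms. Within the SAP, where 6.3.1 and 6.4 list covariates, silence in 6.5 means either no adjustment or a choice left open until the data are seen.
- **Low correlation.** Baseline scores follow usual smoking. Lab scores follow overnight abstinence, and the lab CES, PHRS and CPT concern a different, blinded cigarette. R² may be small; at 0.04 the gain is about one percentage point of power.

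A reader might also infer more than the documents support:

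- **That every secondary-aim rating has a score before study product.** The vaping-device CES and PHRS ratings do not.
- **That precision is lost for all three factors.** The mixed model already removes stable response style from the e-cig contrasts.
- **That the protocol fixes raw differences as the outcome.** Its wording names the aim for three scales; an adjusted post-use score answers it too, and SAP 6.5 does not mention change. The figures in step 3 are therefore conditional.
- **That the arm contrast is underpowered.** Putting the ES of 0.5 into the two-group test gives 77.5%, but 0.5 is the plan's within-subject value. The between-group value is 0.60.

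**Conclusion.** The concern stands in a limited form. SAP 6.5 leaves out stratification variables and pre-randomisation scores that are already collected, and this gives up precision for the NNC versus VLNC contrast alone.

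At one session the gain over an unadjusted score runs from about 1 to 7 percentage points of power (90.3% to between 91.4% and 97.4%) for assumed R² of 0.04 to 0.30. Over the mean of four sessions it could be larger. If raw changes were used for QSU, MNWS and PANAS, the gain from adjustment would be 15% to 35% of the variance for correlations from 0.7 down to 0.3. All these sizes rest on assumed correlations. The omission itself can be read directly from the text.

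**What to change.** In SAP 6.5:

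- Add the stratification variables and, where a pre-randomisation version exists, the Screening/Baseline score as a covariate. For the study-cigarette CES, PHRS and CPT this is the usual-brand or general version. A Session 1 post-sampling rating should not serve as baseline, because it follows use of the assigned cigarette.
- For QSU, MNWS and PANAS, define the outcome as the post-sampling score, after cigarette sampling and after vaping sampling, with the Screening/Baseline or Session 1 pre-task score as covariate instead of a raw change.
- If same-session pre-task scores are used to sharpen the e-cig contrasts, enter them only as deviations from the person's own mean, or in a separate model. In Sessions 2–5 they follow randomisation and exposure to the assigned cigarette; entered raw, they would condition the arm effect on a post-randomisation value.
- State that the vaping-device CES, PHRS and CPT ratings have no baseline covariate.

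The cost is SAP wording and, beyond the stratification variables, one or two covariates per model. No new data are needed. As the SAP is marked final, record the change as a dated amendment, and label it post hoc if the arm comparisons have already been seen.

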6.6. Safety

AEs and SAEs will be recorded as described in the Adverse Event SOP. AEs and SAEs will be tabulated and compared between the two cigarette groups. We expect AEs and SAEs to be extremely rare in this trial and, therefore, no formal statistical comparison of the rate of AEs and SAEs across treatment groups is planned for this trial.

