At the end of Lab Session 1, participants will be presented with the vaping device and oriented on how it will be used during Lab Sessions 2-5. The participant will watch an instructional video on how to use the device and then the RA will show the participant how to operate the device. Next, participants will be instructed how to puff (start and stop) when signaled by the computer. For this vaping practice, participants will use a flavorless e-liquid with 0 mg/ml nicotine. Participants will not be further instructed regarding puffing unless their initial puffs fail to activate the device, in which case they will be instructed to puff harder (Vansickel et al., 2012).

Sampling e-cigarette flavors

After completing the vaping practice, participants will sample the e-liquid flavors. Vaping devices containing e-liquids with 0 mg/ml nicotine in the cigarette and non-cigarette flavors will be sampled. Participants will take a few puffs from each e-liquid flavor and then will select one flavor from the cigarette-flavor category and one flavor the non-cigarette flavor category to use in subsequent sessions. The nicotine concentration of the e-liquid used in this session (0 mg/ml) differs from those used in future sessions to avoid affecting choices during future session.

Researchers will complete the End of Visit Evaluation Form, which will be entered into REDCap.

Lab Sessions 2-4 Procedures

Lab Sessions 2-4 should be scheduled at a minimum interval of 48 hours apart and ideally no more than one week later. Every attempt will be made to schedule participants at approximately the same time of day as Lab Session 1 (\pm 2 hours). If participants are not able to attend within the ideal scheduling window, the session will be scheduled on the next available day outside the ideal scheduling window. If a longer interval is needed between sessions, the RA will contact the PI or Project Coordinator for approval. All sessions will be scheduled consecutively and no session will be skipped unless otherwise informed by the PI or project coordinator. Participants will arrive at each session having abstained from smoking sufficiently to achieve a breath CO level that is \leq 5 ppm or \leq 50% below the CO level obtained at screening/baseline.

Physiological measures collected, recorded on paper, and entered into REDCap by the interviewer at the end of the visit:

- 1) CO
- 2) Blood Pressure
- 3) Heart Rate
- 4) Urine pregnancy test, if applicable

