The following assessments will be administered as an interview and entered into REDCap by the interviewer:

- 1) Concomitant Medications Form
- 2) Health Changes Questionnaire
- 3) Adverse Event Form, if applicable
- 4) TLFB Questionnaire

PRE-TASK assessments will be administered using Qualtrics or REDCap:

- 1) MNWS
- 2) QSU-10 Usual Brand Version
- 3) PANAS

Sampling Phase Procedures

In the *Sampling Phase* (35 min), participants will be oriented to task procedures and shown the products available for that session. In Lab Sessions 2 through 5, two products will be available: (a) cigarettes (NNC or VLNC) and (b) vaping devices containing e-liquids with the assigned nicotine concentration and flavor characteristics for that session. Participants will have selected their e-liquid flavors during Lab Session 1.

Once the task begins, all instructions will be delivered via computer; sessions will be continuously observed by a research assistant through a one-way mirror. Participants will be prompted via computerized instructions to take four timed puffs of the cigarette and then complete the Product Rating Forms. Following a 15-min delay to allow the effects of the cigarette to dissipate, participants will be prompted to take four timed puffs of the vaping device and then complete the Product Rating Forms, followed by another 15-min delay prior to the *Preference Phase*. During protocol breaks, participants will be allowed to watch TV or read magazines.

Product Rating Forms will be administered using Qualtrics or REDCap immediately after sampling the product:

- 1) MNWS
- 2) QSU-10 Usual Brand Version
- 3) PANAS
- 4) CES – Study Cigarette and Vaping Device Versions
- 5) PHRS – Study Cigarette and Vaping Device Versions
- 6) CPT – Study Cigarette and Vaping Device Versions

Preference Phase Procedures

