*Legend:

RN	Reduced Nicotine
RN-Men	Reduced Nicotine-Menthol

CN	Conventional Nicotine
CN-Men	Conventional Nicotine-Menthol

Vaping Device to be used in this study

All participants will use the same device type. The device will be an ego vaping device with a 650 mah battery with a 2ml tank clearomizer. These clearomizers are disposable and will be pre-filled by a staff member. E-liquid will differ across Sessions 2-5. All e-liquid will be purchased from a United States manufacturer and wholesale distributor of e-liquid, and will contain 70% Propylene Glycol and 30% Vegetable Glycerin. Nicotine concentration will be either 0 mg nicotine/ml (used during e-liquid flavor sampling), 3 mg nicotine/ml, or 18 mg nicotine/ml. Two cigarette flavor options will be available (e.g. "light" tobacco, and tobacco/menthol) and four non-cigarette flavor options will be available (e.g. fruit, candy, and vanilla). A flavorless e-liquid option will be used while participants are familiarizing themselves with the vaping devices.

Product Distribution

The Administrative Core will be responsible for removing all identifying information from cigarettes, blinding the cigarettes for the research staff, and shipping cigarettes to our site as needed based on recruitment. The participants, investigators, and study staff will not have knowledge of which cigarette is given to a participant or whether different participants received the same or different cigarettes.

The Administrative Core will ship the e-liquid products to our site as needed based on recruitment. Because participants will be selecting their e-liquid flavors during Session 1, a staff member who is not involved in participant enrollment will create e-liquid kits that include the appropriate flavors and nicotine concentrations based on the randomization schedule generated by the Administrative Core. The participants, investigators, statisticians, and study staff working with participants will not have knowledge of which e-liquid nicotine concentration is given to a participant during each laboratory session.

The site will be responsible for tracking all tobacco products received and used by participants during the lab sessions.

Participant Compensation

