Participants are free to discontinue at any time and will receive compensation for the sessions completed at the same rate listed below. They will receive payment on the date when they would have completed the study. However, they will not receive the fixed bonus for attending all sessions. Study compensation will be administered to participants using the ClinCard payment system utilized by Brown University.

Screening- Eligibility Only	\$ 35.00
Baseline	\$ 35.00
Sessions 01-05	\$ 375.00
Completion Bonus	\$ 125.00
Total	\$ 570.00

Quit Attempts During the Study

At each lab session, we will assess cigarette smoking use via the TLFB. If the participant does not report

smoking any cigarettes on the TLFB, then the research assistant will ask the participant if she/he is currently abstaining with the intention of quitting for good.

If a Participant is Currently Abstaining from Smoking with the Intention to Quit:

- Encourage participant to continue abstaining from smoking
- Provide the participant with the 'Kick the Habit' manual and local smoking cessation resources
- Pay participant for visit attendance and end the visit.
- Participant will be withdrawn from the study.

Adverse Events and Withdrawal or Monitoring of Participants

Identifying Adverse Events

While participating in the study, adverse events and concomitant medications will be assessed at every study visit and vital signs and carbon monoxide will be obtained. Adverse events will typically be identified during the administration of the Health Changes Questionnaire. Other events may be identified from physiological study measures or by spontaneous reports during non-scheduled assessments.

Questionnaire items that will be reviewed:

- 1) *Have you had any negative changes in your physical or mental health since your last visit? If yes, briefly describe.*
- 2) *Since your last visit, have you received any form of medical care? If yes, briefly describe.*

No new AE required if one or more conditions below are met and the description does not otherwise meet the definition of an AE.

- a. Existing AE already open for reported symptom
- b. Pre-existing condition without increase in severity or frequency of symptoms (brief medical history will be updated if not previously reported).
- c. Received preventative or follow-up medical care.
- d. Other (explain).

Physiological data that will be reviewed:

- CO level: The 'Adverse Event Form' should be completed if the average CO within a visit is:

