3.1. Randomization

Randomization will be done in two stages. In the first stage, each individual will be randomized in a 1:1 ratio to either the normal nicotine content (NNC) or the very low nicotine content (VLNC) cigarettes in a double blinded fashion. The randomization will be stratified by gender, menthol status and cigarettes per day (<9, 9+). The goal is 60 subjects per cigarette group. The second randomization stage will be done within the subjects. Individuals in the two cigarette groups will be assigned to all four combinations of sessions involving e-cigs (flavor and nicotine content each at 2 levels) in counter balanced order, which provides 24 possible orders for the four e-cig sessions. The no e-cig session will always be first followed by the e-cig sessions, in an order randomly chosen from one of the 24 possible orders without replacement. Once all 24 session orders have been exhausted, the process will start over with another set of 24 orders. Each cigarette group (n=60) will end up with the same arrangement of the four sessions occurring 2 to 3 times. This will not allow for the evaluation of an order effect in the data analysis, but it will prevent a systematic bias due to the arrangement of the sessions.

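### SAP 6.6 tabulates adverse events by cigarette group alone, so the planned table does not separate them by the e-liquid factors randomised within person

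*Combined protocol and SAP*

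**What the plan says.** SAP 6.6 gives one layout for safety data: "AEs and SAEs will be tabulated and compared between the two cigarette groups". It adds "We expect AEs and SAEs to be extremely rare in this trial" and on that ground plans no formal comparison. I found no AE summary by session, e-liquid concentration, flavour or e-cig availability elsewhere in the SAP or the protocol.

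SAP 3.1 makes the e-liquid factors within-person: "Individuals in the two cigarette groups will be assigned to all four combinations of sessions involving e-cigs", in counterbalanced order, after a first session whose task offers cigarettes only. The protocol's description of the vaping device states: "Nicotine concentration will be either 0 mg nicotine/ml (used during e-liquid flavor sampling), 3 mg nicotine/ml, or 18 mg nicotine/ml".

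Exposure to the assigned e-liquid does not depend on choice. In the sampling phase of each e-cig session (protocol, Lab Sessions 2-4 Procedures; Session 5 follows the same procedures), "participants will be prompted to take four timed puffs of the vaping device".

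On collection, the protocol's Identifying Adverse Events section says "adverse events and concomitant medications will be assessed at every study visit". The main prompt is "Have you had any negative changes in your physical or mental health since your last visit".

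**The concern.** The study manipulates three factors, and the safety table is laid out by one of them. The other two vary inside each participant, so a column for a cigarette group pools that group's events after 3 mg/ml and 18 mg/ml and after both flavour types. If one e-liquid were followed by more events to a similar degree in both groups, both columns would rise together and the comparison between them would look unremarkable.

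At stake is descriptive tolerability information on the e-liquids in 15- to 20-year-olds. The protocol's own risk section lists common side effects of vaping and symptoms of excess nicotine. The primary and secondary endpoints are analysed by the full 2 x 2 x 2 layout (SAP 6.3.1 and 6.4). AEs are not.

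**Working it through.** **Any figure to reproduce.** The plan states no AE rate and no safety precision. Its sample-size figure (SAP 3.2: 60 per group, effect size 0.60, two-sided 0.05, at least 90% power) concerns puffs. It reproduces at 0.903 with the noncentral t. It matters here only because 60 completers per group set the denominators.

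**Inputs from the documents.**
- 60 completers per group, 120 in total (SAP 3.2).
- Five sessions each: Session 1, two at 3 mg/ml and two at 18 mg/ml (SAP 3 and 3.1).
- Sessions per e-liquid condition: 120 x 1 = 120. Sessions per nicotine level: 120 x 2 = 240.
- Vaping puffs per e-cig session: 4 sampled, plus 0 to 20 chosen, so 4 to 24.

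**What the planned table shows.** Let p1, p3 and p18 be AE rates per session, assumed equal in the two groups.
- Expected events in each column = 60 x (p1 + 2 x p3 + 2 x p18).
- Expected events by concentration, both groups together = 240 x p3 and 240 x p18.

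The rates below are assumptions, chosen to span a range:

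| p1, p3, p18 | Each cigarette group | 3 mg/ml | 18 mg/ml |
|---|---|---|---|
| 1%, 1%, 5% | 60 x 0.13 = 7.8 | 2.4 | 12.0 |
| 2%, 2%, 8% | 60 x 0.22 = 13.2 | 4.8 | 19.2 |
| 2%, 2%, 10% | 60 x 0.26 = 15.6 | 4.8 | 24.0 |

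A four- to five-fold difference between concentrations gives an expected column difference of zero in each row. That zero follows from assuming the same rates in both groups. It does not hold in general.

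**Zero-event bounds.** With no events, the one-sided 95% upper bound on the rate is 1 - 0.05^(1/n).
- One e-liquid condition, n = 120 participants: 1 - 0.05^(1/120) = 2.5%.
- One nicotine level, n = 240 sessions: 1 - 0.05^(1/240) = 1.2%, only if a person's two sessions are independent. If events cluster fully within person, the bound returns to 2.5%.

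**Whether the data allow a split.** AEs are asked about at every visit, and the e-liquid order comes from a randomisation schedule, so events can be linked to conditions. Three details decide how:
- The question covers the period since the previous visit. An event reported at Session 3 may have followed the Session 2 e-liquid, so splitting by visit of report would misplace it.
- Session 1 is not free of vaping. After a flavourless 0 mg/ml practice, "Vaping devices containing e-liquids with 0 mg/ml nicotine in the cigarette and non-cigarette flavors will be sampled". It is also always first, so it is confounded with order.
- The 30-day call is described as covering AE forms still open. New events after Session 5 may be missed. Counterbalancing spreads that loss roughly evenly over the four conditions.

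**Whether another analysis fills the gap.** SAP 6.5 models heart rate and blood pressure across sessions. These are not AEs, and the visit procedures list them before product use; the post-task list contains only CO.

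**The case against.** The case against is substantial, and much of it limits what can be claimed.

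- **A reader might infer that the cigarette-group table gives no bound on e-liquid event rates.** It can. Zero events in both columns means zero in every e-liquid condition, so the bounds above follow from the planned table and the session counts. With k events in total, no condition can have more than k. With AEs expected to be very rare, this is a realistic case.
- **A reader might infer that any e-liquid difference falls equally on both columns.** That needs similar e-cig use in the two groups and no interaction. Chosen puffs can take vaping from 4 to 24 per session, and the protocol's rationale is that low-nicotine cigarettes may move smokers towards e-cigs. An e-liquid effect could then appear as a group difference, and the table would give no means of telling it from a cigarette effect.
- **A reader might infer that the trial could not report AEs by e-liquid.** It could. The data are collected by visit, and the table can be made afterwards. What is missing is the advance specification.
- **Attribution is weak.** Sessions are at least 48 hours apart, participants return to usual tobacco use between them, daily vapers are eligible, and every e-cig session also includes the study cigarette. This stands as a limit on the added table.
- **The plan may say more elsewhere.** SAP 6.6 refers to an Adverse Event SOP that is not in the documents. It is cited for recording AEs, not for tabulating them. That no other AE table is planned remains an inference from silence.
- **No safety aim by e-liquid is stated, and subjective response is collected after each product is sampled.** This is true, and it makes the point an improvement, not an error. It does not supply AEs by e-liquid. Expected rarity likewise justifies having no test, but not leaving out a descriptive split.

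**Conclusion.** The point holds as a modest reporting gap. The one AE table in the SAP is by cigarette group, it does not separate events by the two e-liquid factors, and an e-liquid effect similar in both groups would not show as a difference between its columns. In the assumed scenarios, 2.4 against 12.0 events by concentration corresponds to 7.8 against 7.8 by cigarette group.

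This rests on three assumptions: the illustrative rates, equal rates in the two groups, and 120 completers each contributing five sessions. The documents do not support going further, to say that the planned table is uninformative about e-liquids or that the comparison is lost. The primary and secondary analyses are untouched. It is worth doing because it is cheap and uses factors the trial already randomises.

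**What to change.** Keep the cigarette-group table. Add to SAP 6.6 one descriptive table of AEs and SAEs, without formal tests:

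- **Rows:** condition of the most recent session before onset, that is Session 1, then 3 or 18 mg/ml by cigarette or non-cigarette flavour. List separately any event with onset before first use of a study product.
- **Columns:** each cigarette group and overall.
- **Contents:** number of events and number of participants with an event, with participants exposed and sessions given as denominators.
- **Label:** call the reference level Session 1, not no e-cig, and footnote that it ends with 0 mg/ml vaping and always comes first.
- **Attribution rule:** assign by onset, not by visit of report. The protocol's description of the AE form mentions neither onset date nor product, so confirm that onset is recorded.
- **Bounds, if reported:** state that they are one-sided 95%, and that the 240-session figure assumes independent sessions.

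The cost is one extra table and a short attribution rule. The drawback is that attribution stays approximate: usual products are used between sessions, the study cigarette is present at every e-cig session, and new events after Session 5 may be under-captured. A footnote should say so.
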